The present study will recruit 25 male adolescents between the ages of 13 and 17 years. Participants will be recruited via advertisements in the community (e.g., grocery stores, fitness centers, restaurants), at CHEO, and through word of mouth. Volunteers will be excluded for any of the following reasons: smoking, unstable body weight (± 4 kg) during the 3 months preceding testing, excessive alcohol intake (>15 drinks/week), celiac disease, metabolic disease (e.g., thyroid disease, heart disease, diabetes), medication use that could interfere with the outcome variables, highly restrained eating behavior (score of ≥ 12 for cognitive dietary restraint on the Three-Factor Eating Questionnaire), irregular sleeping pattern (e.g., shift work or working overnight shifts), and inability to comply with the protocol. Following a phone call with the potential participant to confirm eligibility and explain the study, consent forms will be mailed and

will need to be returned to us in the pre-paid envelope provided before any testing can begin. Participants who are capable of consenting will be asked to do so on their own behalf; otherwise, written informed parental consent and child assent will be obtained. Ethical approval will be obtained from the Children's Hospital of Eastern Ontario Research Ethics Boards. Participants will receive \$30 per condition for their participation in the study (\$120 total).

Overview of the Study Protocol

Preliminary Visit

The participants will attend one baseline session and three experimental sessions, each separated by at least one week. All sessions will begin at 07:30, and the participants will be instructed to fast and abstain from structured exercise for 12 hours before each visit. The preliminary visit will include measurements related to anthropometry (body weight, height, waist circumference), resting metabolic rate and cardiorespiratory fitness (VO_2 peak). Participants will also complete questionnaires in order to better characterize them. During this initial visit, participants will be asked to identify any food allergies or intolerances that might impact the standardized breakfast and buffet meals provided during the experimental sessions.

Experimental Sessions

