Each participant will be engaged in each of the following three 30-min experimental conditions followed by an *ad libitum* lunch: **(1) walking/jogging on a treadmill at 60% of VO_2 peak while watching a screen (exercise + screen); (2) walking/jogging on a treadmill at 60% of VO_2 peak while listening to music (exercise + music); and (3) walking/jogging on a treadmill at 60% of VO_2 peak with no other stimulus (control condition).** These 3 conditions will be randomly assigned by using a computerized randomization scheme. Participants will be free to watch whatever they want on the screen and listen the music of their choice using a personal music player.

One at a time, on 3 separate occasions, the participant arrives at the laboratory (Children's Hospital of Eastern Ontario Research Institute, Ottawa) at 07:30 after fasting for 12 hours. An accelerometer will be attached immediately on arrival and will be worn until bedtime. Visual analogue scales (VAS) will be used to record subjective measures of appetite at 07:45 (and at other time points during the day), and the participant will be provided a standardized breakfast at 08:00. The participant will then refrain from eating until the *ad libitum* lunch. The 30-min experimental intervention consists of 1 of the 3 conditions, starting at 10:30. Participants will be asked to relax on a comfortable chair between the end of the breakfast and the beginning of the testing condition. After the experimental condition, an *ad libitum* test lunch will be given to the participant to evaluate spontaneous food intake. A dietary record will be used to assess food intake for the remainder of the day. A schematic overview of the study protocol is presented in the Appendix.

Measurements

Anthropometric Measurements

Body weight will be measured without shoes in light clothing, after voiding, to the nearest 0.1 kg on a calibrated electronic scale. Height will be measured to the nearest 0.1 cm with the participant standing against a wall-mounted stadiometer, feet together, without shoes and with the head in the Frankfort plane, after a deep inspiration. Body mass index (BMI) will be determined and interpreted with the WHO BMI-for-age growth charts (11). Waist circumference will be measured to the nearest 0.1 cm using a non-extendable linen tape and measured midway between the lower border of the last rib and the upper border of the iliac crest at the end of a normal expiration.

Breakfast

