For each condition, the participants will be instructed to complete 9 VAS for their sensations of hunger, satiety, prospective food consumption, fullness, and desire to eat something sweet, salty, or rich in fat. They will also rate their opinion on the general appreciation of the meal and on the overall satisfaction/enjoyment of the experimental conditions, from “extremely boring” to “extremely pleasant”. The VAS is a line (100 mm in length) with statements anchored at each end expressing the most positive and most negative rating of the participants’ appetite sensations. The VAS have been shown to be both reproducible and valid for measurement of appetite sensations in a laboratory setting (14). The VAS will be completed during each experimental condition: at fasting (07:45), before the experimental condition (10:25), immediately after the experimental condition (11:05), and immediately after the *ad libitum* lunch.

Dietary Record

All participants will be instructed to complete a dietary record (15), with help from the parents, after each experimental condition to evaluate the degree of potential compensation in food intake for the remainder of the day. Participants will be instructed on how to complete the dietary record and on how to measure quantities of ingested foods. The food records will be reviewed with each participant upon their return to improve the validity of the information provided. Mean energy and macronutrient intakes will be calculated by using the Food Processor SQL software (version 9.6.2; ESHA Research).

Resting Metabolic Rate and Cardiorespiratory Fitness Measurements

Resting metabolic rate (RMR) will be measured during the preliminary visit by indirect calorimetry (Vmax 229 series metabolic cart; SensorMedics). RMR will be measured for 30 min after a 30-min rest period and a 12-h overnight fast. The first and last 5 min will be excluded from the calculations; thus, minutes 6-25 will be used in the calculation. Mean RMR will be calculated by using the Weir equation (16). VO_2 peak will be measured using the same metabolic cart and using the Dubowy graded treadmill protocol (17). Exercise sessions on the treadmill will be set at 60% of VO_2 peak (moderate-intensity physical activity).

Perceived Exertion

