Ratings of perceived exertion (RPE) will be used to quantify participants' perceived exertion during the experimental conditions by using the OMNI scale of perceived exertion. The scale ranges from 0 (extremely easy) to 10 (extremely hard) and has been previously validated in the pediatric population (18). Participants may find the exercise session easier to perform with the use of a stimulus (e.g., music or TV program). It is also possible that the RPE may influence post-exercise energy compensation. Participants will rate their RPE at every 5 min during the conditions and the area under the curve (AUC) will be calculated using the trapezoid method.

Physical Activity Energy Expenditure Compensation

Changes in physical activity after each condition will be assessed by using an Actical accelerometer (Philips Respironics). The accelerometer, on an elastic belt, will be positioned on the right iliac crest in midaxillary position immediately on arrival at the laboratory (07:30) and worn until bedtime. The Actical measures and records time-stamped acceleration in all directions (omni-directional), and the digitized values are summed over a user-specified interval of 1 minute. The Actical has been validated to measure physical activity in children and adolescents (19) and has better instrument reliability than other accelerometer models (20). Accelerometry data will undergo standardized quality control and data reduction procedures, as previously reported (21). Physical activity energy expenditure (PAEE) will be determined from the Actical by using validated equations (19).

Questionnaires

To better characterize the adolescents, some questionnaires will be administered during the preliminary visit. The 51-item Three-Factor Eating Questionnaire (22) will be used to

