verify that the participants are not restrained eaters (those with a score ≥ 12 for cognitive dietary restraint will not be eligible). The purpose of this questionnaire is to assess 3 factors related to cognition and eating behaviours: cognitive dietary restraint (intent to control food intake), disinhibition (overconsumption of food in response to cognitive or emotional cues), and susceptibility to hunger (food intake in response to feelings and perceptions of hunger). This questionnaire has been validated, and its 3 scales have been reported to show good test–retest reliability (23). In addition, participants will complete the Pittsburgh Sleep Quality Index (24), a self-rated questionnaire that assesses sleep quality and disturbances over the preceding month. Sleep hygiene will be assessed in this study because sleep has been shown to influence appetite sensations (25). A total score >5 is associated with poor sleep. The physical activity pattern of participants will be assessed by using the Physical Activity Questionnaire for Adolescents, a self-report measure of physical activity that has been validated in white Canadian samples (26). A score of 1 and a score of 5 indicate low and high physical activity participation, respectively. Finally, the pubertal status of adolescents will be evaluated with a self-assessment questionnaire that aims to measure pubertal status by using gender-specific line drawings of the Tanner puberty stages (27).

POTENTIAL RISKS

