Before statistical analysis, all data will be tested for normality by using the Shapiro-Wilk W test and variance homogeneity and will be log-transformed if necessary. Repeated measures analysis using the mixed model will be used to assess the effect of the 3 interventions on outcome measures, with effects for age, condition, pubertal status and BMI. The models will be adjusted for covariates if they are found to significantly interact with the outcome variables. To account for the fact that repeated measures are taken across conditions, the models will include a participant-specific random effect. Effect sizes will be examined by using the Cohen's *d* method, reflecting the magnitude of the difference between groups in SD units. Cohen's *d* is computed by subtracting the average score of the control group from the average score of the intervention group and then dividing the difference by the pooled SD. Effect sizes are considered negligible if <0.2 , small if between 0.2 and 0.5, moderate if between 0.5 and 0.8, and important if >0.8 . Correlations will be used to examine if the RPE are associated with post-exercise energy compensation. Differences will be considered significant at $P < 0.05$ and data will be presented as mean values and SDs. All statistical analyses will be performed by using SPSS Statistics 23.0 (SPSS Inc, Chicago, IL, USA).

FACILITIES AND EQUIPMENT

The present project will be carried out in our facilities at the Children's Hospital of Eastern Ontario Research Institute in Ottawa. As a national centre of excellence for research, leadership, training and advocacy, our research group strives to provide international leadership and research excellence as it relates to healthy active living and obesity in children and youth (www.haloresearch.ca). All of the proposed methods are routinely performed in our laboratories and the research staff is highly qualified for the

purpose of the study. The personnel needed for this study and the infrastructure and equipment required to conduct the research is available and accessible. The main investigators involved in the proposed research project are also very experienced in designing and conducting studies in this field of research.

KNOWLEDGE TRANSLATION APPROACH

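### The same-day 10:25 appetite rating is not named as a covariate for the appetite outcomes; pre-specifying it is a free, possibly small, gain in precision

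*Combined protocol and SAP*

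**What the plan says.** Outcome Measures lists appetite ratings and perceived exertion (RPE) as the secondary outcomes. Under Appetite Sensations, ratings are made in each session while fasting at 07:45, then "before the experimental condition (10:25), immediately after the experimental condition (11:05", and again after lunch. Experimental Sessions fixes the start: "The 30-min experimental intervention consists of 1 of the 3 conditions, starting at 10:30". The 10:25 rating is therefore a same-day baseline taken before that day's exercise.

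Statistical Analysis describes one repeated-measures mixed model for all outcomes, "to assess the effect of the 3 interventions on outcome measures, with effects for age, condition, pubertal status and BMI", with a participant random effect. It then adds a selection rule: "The models will be adjusted for covariates if they are found to significantly interact with the outcome variables". No appetite rating is named as a covariate, and the section does not say which of the four ratings is the outcome.

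BMI and pubertal status are each obtained once. "The preliminary visit will include measurements related to anthropometry (body weight, height, waist circumference", and under Questionnaires "some questionnaires will be administered during the preliminary visit", among them the one by which "the pubertal status of adolescents will be evaluated with a self-assessment questionnaire".

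For perceived exertion the plan says only: "Correlations will be used to examine if the RPE are associated with post-exercise energy compensation".

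**The concern.** In a crossover the condition effect is estimated from differences between sessions of the same boy. A covariate that takes one value per boy cancels from those differences. Age, pubertal status and BMI are of that kind (age moves by only weeks), so the named covariates do nothing for the precision of the comparison that matters. The covariate that varies from session to session, and is recorded just before exercise, is not named.

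What is at stake is precision for a secondary outcome in a trial of 25 boys. Validity is not in question.

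The RPE sentence leaves a smaller gap. Each boy supplies three pairs of RPE and compensation, and the plan does not say whether the unit of analysis is the boy, the boy within one condition, or the session.

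**Working it through.** **Inputs from the documents.** 25 boys, 3 sessions each, hence 75 sessions; ratings at 10:25 and 11:05; condition starting at 10:30; named effects as quoted. The plan gives no precision or power figure for appetite (its sample-size statement concerns energy intake and expenditure), so there is no stated figure to reproduce.

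**Assumed.** The within-boy correlation r between the same-day 10:25 rating and the post-condition rating, taken from 0 to 0.7; complete data.

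**Step 1: covariates with one value per boy.** Write the rating of boy i under condition j as y_ij = τ_j + βz_i + b_i + e_ij. Then y_ij − y_ik = (τ_j − τ_k) + (e_ij − e_ik): the term βz_i drops out. In fitted mixed models with three such covariates, the standard error of the contrast changed by a factor of 1.000 at every r tried.

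**Step 2: adding the 10:25 rating.** With condition and boy effects the error degrees of freedom are 75 − 25 − 2 = 48. Adjustment removes a share r² of the within-boy residual variance. Estimating the slope costs on average a factor 1 + 1/(48 − 2) = 47/46. So

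variance ratio = (1 − r²) × 47/46, and SE factor = its square root.

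| Assumed r | Variance ratio | SE factor, formula | SE factor, simulated | Equivalent boys (25 ÷ variance ratio) |
|---|---|---|---|---|
| 0 | 1.022 | 1.011 | 1.011 | 24.5 |
| 0.1 | 1.012 | 1.006 | 1.006 | 24.7 |
| 0.3 | 0.930 | 0.964 | 0.964 | 26.9 |
| 0.5 | 0.766 | 0.875 | 0.876 | 32.6 |
| 0.7 | 0.521 | 0.722 | 0.722 | 48.0 |

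The simulation used 8,000 trials per value of r, with period also in the model. The mean contrast stayed within 0.01 of zero and the type I error was 0.046 to 0.053. A contrast with 80% power unadjusted would have 79%, 83%, 89% and 97% at r = 0, 0.3, 0.5 and 0.7.

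**Step 3: if the selection sentence reached the 10:25 rating.** Read it as a 5% test of the covariate. The rating is then kept in 5%, 10%, 55%, 96% and 100% of trials at r = 0, 0.1, 0.3, 0.5 and 0.7, and the type I error remains about 5%. The SD of the contrast under test-then-include, relative to always including, is 0.993, 0.996, 1.008, 1.017, 1.014, 1.003 and 1.000 at r = 0, 0.1, 0.2, 0.3, 0.4, 0.5 and 0.7. Under that reading pre-specification gains less than 2% anywhere, and loses less than 1% at r of 0 to 0.1.

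**The case against.** The strongest reply is that the factors in the table compare always including the rating with never including it, and the plan does not commit to never. Its selection sentence excludes no covariate, and if it were applied to the 10:25 rating it would deliver nearly all the gain at r of 0.5 or more (step 3). That stands, and it limits the size of the point. But the sentence lists no such covariate, comes directly after age, pubertal status and BMI, and leaves its criterion undefined. It cannot be relied on to bring the rating in.

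It is also fair to say that r may be low. The overnight fast, the identical breakfast and the seated rest already standardise the pre-exercise state, which may leave little within-boy variation at 10:25 to adjust for. That stands too, and is why the range includes zero.

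A reader might infer that the omission biases the appetite comparison. It does not: the unadjusted contrast is unbiased and holds its error rate.

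A reader might also infer that the RPE correlations are invalid or underpowered. The documents support neither.

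- Correlations within each condition (n = 25) are valid.
- False-positive rates of 7%, 11% and 17% (both intraclass correlations at 0.3, 0.5 and 0.7) arise only if 75 rows are pooled as independent, which the plan does not state.
- A within-boy analysis is more powerful under some assumptions and not others. With a within-boy correlation of 0.3 and no between-boy link, power is about 55%, against 7 to 17% for one per-condition correlation. With 0.2 within boys and 0.4 between boys it is 28% against 30% (intraclass correlation 0.5) or 27% against 39% (0.7).
- The plan asks only about association, so a between-boy reading is legitimate.

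**Conclusion.** The point holds as a minor, cost-free improvement to a secondary analysis. The plan names three covariates that do not sharpen the within-boy condition contrast and does not name one, already scheduled, that may. Against leaving the 10:25 rating out, the SE factor is about 0.96, 0.88 or 0.72 at r = 0.3, 0.5 or 0.7, and about 1.01 at 0 to 0.1. Against applying the selection sentence to it as a 5% test, the gain is under 2%. Which comparison applies cannot be settled from the text, and every r is an assumption. All figures assume that 25 boys complete three sessions.

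There is no bias in the plan as written, and the primary outcome is not affected. On RPE the documents support only a request to state the unit of analysis; no power advantage should be claimed for either approach.

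**What to change.** **Appetite.** For each appetite scale, pre-specify a mixed model for the post-condition rating with condition, the same-day 10:25 rating, the boy's mean 10:25 rating and the participant random effect. Keep the 10:25 terms whatever their significance. The boy's mean separates the within-boy slope from differences between boys. State which post-condition rating is the outcome; 11:05 is the natural choice for the direct effect of the condition. The covariate has no counterpart for meal appreciation, enjoyment of the session or RPE, which have no pre-condition rating.

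**Perceived exertion (optional).** State the unit of analysis for the correlations and rule out treating 75 sessions as independent. If the within-boy question is intended, regress compensation on participant-centred RPE AUC and participant-mean RPE AUC, with condition and a participant random effect, labelled exploratory. Condition must stay in the model. In simulations where a stimulus lowered RPE by one within-boy SD and raised compensation by 0.25, 0.5 or 1 SD, with no true RPE effect, omitting condition gave false-positive rates of 8%, 17% and 44%; including it gave about 5%.

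**Cost.** A few sentences of analysis text. No visit, rating or participant is added. If the 10:25 rating proves unrelated, the standard error rises by about 1%.
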